12. STUDY MONITORING

12.1 Steering Committee

The steering committee will include: [name] (Institute of Psychiatry), [name] (Collaborator, National Autistic Society), representatives from the local National Autistic Society, [name] (Parent Representative), [name] (Parent Representative), [name] (CI), [name] (Statistician), and other team members as appropriate.

The steering committee will be consulted on the final design of the follow-up, techniques for ascertainment and the focus for measurement. We will have a particular focus on ascertaining families' experience and quality of life using our new measure, the FLQ, developed at MRC request within the PACT trial.

12.2 Project management and data monitoring group

The project management group will be chaired by [name] and consist of the Principal Investigators and senior researchers on the study and other invited members as necessary. It will meet quarterly.

12.3 Monitoring and indemnity

The study will be subject to the audit and monitoring regime of the University of Manchester. The University of Manchester will arrange insurance for research involving human subjects that provides cover for legal liabilities arising from its actions or those of its staff or supervised students, subject to policy terms and conditions.

12.4 Conflicts of interest

None of the participating PACT families or children are seen clinically by members of the research team

13. DISSEMINATION

The results of the research will be targeted for publication in peer-reviewed journals of general and special interest. There will also be a general dissemination programme for families including participants co-ordinated through our collaborators in the National Autistic Society. For the families and local referring clinicians involved in the study, we send 6-monthly newsletters updating them on the progress of the study, when the findings will be published and other locally and nationally relevant autism 'news'. A written summary of the study results will be sent to all participants in the form of a newsletter at the end of the study. We will publish our findings on the study website (http://www.bbmh.manchester.ac.uk/pact/). We will also disseminate results through local clinical teams (by whom the original PACT referrals were made). At the end of the original PACT trial all 3 collaborating sites held local meetings/conference for parents, professionals, service managers and commissioners to disseminate the trial findings. The same range of dissemination events will be arranged via local services and service users for the end of this follow-up study.

A number of the investigators are active nationally and internationally in communication with parents and professionals more widely (for example, [name] and [name] run a Database of children with ASD in the North East (Daslne); this provides an information website, and sends newsletters twice yearly to 1500 families and professionals). Many of the team present regularly at Special Interest Groups for clinical professionals, for example, the London Special Interest Group for speech and language therapists has over 100 members working across the whole of the South East. At key points at the beginning of the study and when its findings are published we will use these mechanisms to communicate with relevant parent and practitioner audiences.

14. FINANCE

MRC research funding - £840,251

15. ETHICAL APPROVAL AND CONSIDERATIONS

15.1 Ethical Approval Information

REC Reference number: 13/NW/0144

15.2 Procedures for minimising negative consequences

In order to minimise disruption and inconvenience to children and parents we will offer a range of options for home/ clinic visits including early evening, weekends, school holidays or during the day. If it is most convenient for children to be assessed during the school day, a letter on headed paper will be sent to the family to justify the child's absence to the school. The balance between the number and length of appointments will be discussed with the parents at the outset to achieve the best balance for them as a family. Researchers will be sensitive to several issues when arranging visits, including family or work commitments, childcare, and time burden on the parent. Parents will be given the option to complete the assessments at a later date if it is felt that they are struggling during the course of the visit.

During interviews researchers will be aware of the fact that they cover topics that parents may find difficult or upsetting. During interviews, researchers will present questions in a sensitive way and offer the parent the chance to take a break or halt the interview if the parent becomes upset. At the end of an assessment researchers will offer the opportunity to debrief if appropriate. Parents who complete the DAWBA online will be provided with a phone number to call the local research team if they have any concerns or questions when completing the DAWBA. The researcher will then support and reassure parents who have concerns or become upset and will seek advice from their supervisor if any serious concerns are raised. Participants will be informed at the start of the Family History Interview (FHI) that researchers will be happy to talk to them about any concerns that arise as a result of the interview, and if they are still concerned, the researcher will signpost to appropriate sources of support, such as consulting their GP. We will also have a named clinician, a member of the PACT team who is familiar with the FHI and Broader Autism Phenotype, that the parent can speak to afterwards, should they wish to speak to someone about their concerns.

The clinic visit will be made as enjoyable and stress-free for children as possible. Parents will be asked to go through the information sheet with the child prior to the visit. The clinic room will be relatively distraction-free. The parents will be able to stay in the room with the child if this is required to avoid distress. Regular breaks will be offered to the child, in discussion with the parent, to accommodate their needs (toileting, snacks, need to move around or have time-out). If it becomes clear at any point that the child has reached their tolerance level, again in discussion with parents, the session will be ended and continued at a later date.

Researchers will receive lone working training prior to commencement of visits and will follow these procedures when visiting homes or other settings. If for any reason it is felt that the risk is higher than acceptable (e.g. from prior knowledge of family or local area; from information gleaned during previous contacts), a second researcher will accompany the first on the visit or alternative plans will be made. All researchers will have a work mobile phone and will be contactable throughout home visits. All staff working on this study will hold a valid Criminal Record Bureau check. Parents will be present or within the immediate vicinity whilst assessments with children are completed in order to protect children and researchers.

16. REFERENCES

1) [name]. [name], T. [name], H. et al (2010). Parent-Mediated Communication-Focused Treatment for preschool children with Autism (PACT); a randomised controlled trial. *The Lancet*, 375(9732), 2152-2160.

PACT 7-11 SUMMARY OF PROTOCOL AMENDMENTS

The following changes have been made to the protocol from v.1 to v3.

Version Number	Date	Section	Amendment
v.2	05.09.13	General Information, 12. Study Monitoring and 13. Dissemination	These sections have been updated to reflect the following changes: new website address; addition of new Research Associate; change to Trial Steering Committee members.
		7. Timeline	The timeline has been changed to allow more time for start-up tasks and staff training (from April 2013 to June 2013).
		8.3. Assessment Procedures and 9.3 Measures	The SF36v.2 Health Survey has been replaced by the Parent Wellbeing Questionnaire. These sections have been changed to reflect this change. Details of the Parent wellbeing Questionnaire have been added.
		8.3. Assessment Procedures and 9.3 Measures	The Manchester Playground Observation Measure (MIPO) has been added to the protocol and new information about this measure has been added in these sections.
v. 3	22.11.13	8.3 Assessment Procedures and 9.3 Description of Measures	The Autism Diagnostic Interview-Revised (ADI-R) is no longer part of the assessment battery and has been replaced by the Social Communication Questionnaire (SCQ) and Repetitive Behaviour Questionnaire (RBQ). Therefore the ADI-R information has been deleted and details of the SCQ and RBQ have been added in these sections.

PACT 7-11 ANALYSIS PLAN FOR THE PRIMARY FOLLOW-UP PAPER

Authors: [name], [name], [name], [name], [name], [name], [name], [name], [name], [name], [name], [name], [name], [name], [name], [name], [name].

Agreed 21/1/15 prior to inspection of follow-up data by treatment group

Appendix 1: Major post application revisions incorporated in this version

Appendix 2: Subsequent revisions occurring post data inspection

Document Revised for publication 29/1/16

STUDY DESIGN AND TRIAL ENDPOINT ANALYSIS

As described in Green et al. (2010).

FOLLOW-UP ANALYSIS

Overall strategy

Intention-to-Treat analysis of original trial/randomization design.

Primary outcomes: ADOS, DCMA, Language composite Secondary outcomes: VABS, RBQ, FLQ, DAWBA, SDQ, SCQ

Analysis goal: to use all the data to obtain good estimates of outcome where possible using growth curve approaches to yield a group difference at the median follow-up age (elaborated in PART A below) or as a simple follow-up difference or latent regression (elaborated in PART B below). No imputation of baseline data required.

Description

Follow-up rates to be described and balance in baseline covariates among those followed up to be described. CONSORT type diagram in on-line supplement.

Table 1 with Baseline and Follow-up mean/proportion/median and SD/range by treatment group for gender, age-at-recruitment, age-at-follow-up, numbers by centre.

Table 2 Follow-up mean/proportion/median and SD/range by treatment group for primary and secondary measures.

Treatment differences to be summarized in a tree-plot like effect size diagram.

PACT 7-11 Office, University of Manchester, [name]

PACT 7-11 Combined Protocol and Analysis Plans with Changes 1/2/16 Page 24

Part A

Growth Curve Analysis model: For **repeated measures** (i.e. those already measured in PACT) treatment group comparisons at the mean age at follow-up based on a piecewise growth curve model with separate correlated pieces over PACT and PACT7-11. Baseline variables for which groups are imbalanced will be included as fixed-effect covariates with interactions of group and time to allow different effects during PACT and PACT7-11. Group differences will be estimated at the median follow-up age.

Primary Outcomes

1. ADOS-2 overall Comparative Severity Score (CSS)². Then report Social Affect and Restricted and Repetitive Behavior Comparative Severity Scores³ descriptively. The numbers completing each ADOS Module will be reported.

Analysis specifics: The follow-up CSS total scores will be analysed together with baseline and trial endpoint CSS scores, as a set of correlated ordinal scales with different thresholds with group main-effect and time by group interaction, with random intercept and random piecewise slopes, covarying for imbalanced baseline variables. Estimated by maximum likelihood missing data will be assumed Missing at Random.

2. DCMA⁴ PCI from PLAY only

Primary: Child initiations as per 2010 paper (proportion of child codes) Secondary: Parent synchronicity as per 2010 paper (proportion of adult codes)

Secondary: Child conversation as a frequency

Secondary: Mutual shared attention.

Analysis Specifics: Coded reliably only in the 8min PLAY session, synchronicity and initiations at baseline, trial endpoint and follow-up will be analysed by using a mixed effects model with random piecewise time slopes and group by time interactions covarying for imbalanced baseline variables. Stata lincom will be used to construct a single effect estimate at the median age of follow-up. Mutual shared attention and conversational frequency will be presented descriptively.

Secondary Outcomes

3. Parent and Teacher VABS standard score

Parent Vineland Adaptive Behavior Composite⁵ at baseline, trial endpoint and follow-up will be analysed by using a mixed effects model with piecewise time slopes and group by time interactions for imbalanced baseline variables. Stata lincom will be used to construct a single effect estimate at the median age of follow-up.

Teacher Vineland Adaptive Behavior Composite at follow-up will be analysed by regression covarying for imbalanced baseline variables.

4. FLQ total score

The Family Life Questionnaire total score will be analyzed in the same manner as Parent VABS, but this measure lacked a published reference.

Part B

For outcomes that are novel to PACT7-11 (i.e. lacking baseline equivalents) group comparisons based on regression/SEM latent regression of PACT7-11 score on imbalanced covariates, age at follow-up and any baseline measure similar to outcome.

Primary Outcomes

5 Language factor composite

Descriptive statistics by group for the CELF⁶ subtests (including number not administered), and 2 One-Word tests⁷ will be given. Using Mplus, a preliminary factor analysis will be described and a jointly estimated factor model with treatment/covariates effects estimated.

Secondary Outcomes

6. Social Communication Questionnaire and Repetitive Behavior Questionnaire totalsRegression of total scores^{8,9} on group covarying for any imbalanced covariates.

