5. STUDY OBJECTIVES

5.1 Primary Objectives

The PACT 7-11 study is designed to address three central questions:

1) Are the changes in developmental processes achieved in PACT sustained at 4-6 year follow up?

This question is a priority because it addresses an important issue of whether time-limited interventions of this kind are sufficient in a persistent developmental disorder, or whether longer or repeated phased interventions are necessary. The question will be answered through follow-up ascertainment of at least 80% of the original PACT Trial sample after 4-6 years in middle childhood, repeating comparable measures from the original trial, including:

- a. parental synchronous communication with the child (the targeted developmental process in the intervention)
- b. child communication initiations with parent
- c. measures of child communication and child and family adaptive functioning.
- 2) Does the enhancement of these early developmental variables result in later positive developmental outcomes in areas expected from theory?

Theory and independent longitudinal observation studies suggest that changing the early variables may impact on a number of specific longer-term outcomes including specifically child language and communication. The follow-up will also test generalised symptom and adaptation outcomes, which show modest effects at trial endpoint, as to whether the endpoint occurred before generalisation occurred. These hypotheses will be tested at follow-up by measuring:

- a. Child communication and language outcomes
- b. Autism symptoms
- c. Parent reported outcomes in child development, parental and family functioning
- d. Burden of parental care and service use
- 3) Can we use a treatment trial of this kind as a 'developmental experiment' to illuminate basic questions in the development science of autism?

The unique strength of this proposal is that the initial randomisation in the PACT trial allows for a causal interpretation of subsequent effects, something that does not apply in observational longitudinal studies. We will thus use the developmental follow-up of randomly allocated parallel cohorts and application of methodological innovations developed within the trial team to test a number of basic science hypotheses in autism:

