10.4 Analysis plan

Primary analysis of the data will take place within the University of Manchester, King's College London or the University of Newcastle, by [name] (Trial Statistician) or [name] (Chief Investigator). Other team members will have access to the data and undertake analyses as appropriate. Any arrangements for other researchers in the general field to have access to the primary data will be negotiated separately and COREC informed.

Stage 1: Preliminary analyses will approach the follow-up data using the traditional Intention-To-Treat method, covarying for baseline values of measures corresponding to outcomes, and for measures of parental educational qualifications and SES baseline factors, identified previously as unbalanced across treatment groups. The primary outcomes will be: language and communication outcomes (CELF, ROWPVT); family functioning (FLQ) and the ADOS, for which we shall make use of the cross-module standardized severity scores (Gotham et al., 2009). Missing data will be multiply imputed, using only imputations of the baseline variables where the analysis model is maximum likelihood (and thus able to exploit properties of ML for ignorable non-response). Analysis will use appropriate generalised linear models, where possible, using models for repeated measures growth curves fitted to baseline, outcome and follow-up. These will characterise not only an overall effect but also the extent to which later effects are consistent with a magnification or attenuation of the early effects observed in the original trial. Having repeated measures will increase our potential power but, for some analyses, we will need to account for multiple testing (the previous PACT findings essentially forming an interim analysis).

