APPENDIX 2: Subsequent revisions occurring post data inspection

During analysis:

- (1) Two secondary outcomes were dropped: i) Mutual Shared Attention from the DCMA interaction coding that had been suggested for descriptive reporting but on later testing in independent middle childhood samples had been found to be unreliable and age-inappropriate; ii) family life score from the FLQ questionnaire for which published validation had not yet become available;
- (2) For the longitudinal models the Area-Under-the-Curve estimates were added as a means of summarizing treatment effect over the course of the study and multiple imputation and GEE/robust standard error estimation was used as an additional check as the robustness of the findings to model misspecification and missing data;
- (3) A proposed Venn-diagram spanning five categories of co-occurring disorders from the DAWBA was dropped as being too disaggregated to be interpretable;
- (4) Bootstrap standard errors were used for the confidence intervals of all effect estimates as their properties were likely to be superior to those based on standard asymptotics for many of the statistics presented;
- (5) The inclusion of dummy variables for centre effects.

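### For repeated measures the SAP names only the group difference at follow-up, so the protocol's question of whether early effects were kept, reduced or enlarged has no named estimate

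*Combined protocol and SAP*

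**What the plan says.** **The question.** Protocol section 5.1, Objective 1, asks: "Are the changes in developmental processes achieved in PACT sustained at 4-6 year follow up". It is given priority because it bears on whether a time-limited therapy is enough or whether longer or repeated phases are needed. Objective 2 adds a related question: whether the trial endpoint came too early for wider effects to have appeared.

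**The protocol's analysis.** Section 10.4, Stage 1, fits growth curves to baseline, endpoint and follow-up. They are to give an overall effect and also "the extent to which later effects are consistent with a magnification or attenuation of the early effects observed in the original trial".

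**The SAP's analysis.** The overall strategy describes the goal as "using growth curve approaches to yield a group difference at the median follow-up age" where growth curves are possible. The Part A introduction repeats it: "Group differences will be estimated at the median follow-up age". Under item 2 (DCMA) and item 3 (parent VABS) this becomes one number: "Stata lincom will be used to construct a single effect estimate at the median age of follow-up". Table 2 is to show follow-up summaries only, and the endpoint analysis is left to the 2010 trial report.

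**The SAP's model.** Part A specifies a "piecewise growth curve model with separate correlated pieces over PACT and PACT7-11", and for the DCMA "random piecewise time slopes and group by time interactions".

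**After data inspection.** Appendix 2, item 2, records that "Area-Under-the-Curve estimates were added as a means of summarizing treatment effect over the course of the study".

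Neither part of the document names a contrast between endpoint and follow-up effects, or a criterion for calling an effect sustained.

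**The concern.** Whether an effect was sustained is naturally a comparison of two treatment effects in the same children, one at PACT endpoint and one 4-6 years later. A follow-up difference read alone answers a narrower question: is a difference present now? The same follow-up value can follow from an endpoint effect that was larger, equal or smaller. For Objective 1 these three histories carry different messages about whether a single course of therapy suffices. If only the follow-up figure is reported, readers must compare it informally with the endpoint result in another paper. That comparison would have no interval for the change and would rest on a different model.

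**Working it through.** **1. What the planned model contains.** Let the group difference at time t be D(t) = b0 + b1·(time in first piece) + b2·(time in second piece), with pieces of length T1 and T2. Then:

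- difference at endpoint = b0 + b1·T1
- difference at follow-up = b0 + b1·T1 + b2·T2
- follow-up minus endpoint = b2·T2

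The planned estimate is the second line. The third line uses a coefficient that is already in it, so it needs no further model.

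**2. Whether the area under the curve fills the gap.** Appendix 2 does not define it, so assume straight pieces and no baseline difference. With endpoint effect e and follow-up effect f, area = ½·e·T1 + ½·(e+f)·T2. Take T1 = 13 months and T2 = 60 months (the middle of 4-6 years, an assumption).

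- Fading, 0.40 to 0.20 SD: ½·0.40·13 + ½·0.60·60 = 2.6 + 18.0 = 20.6 SD-months.
- Growing, 0.20 to 0.443 SD: ½·0.20·13 + ½·0.643·60 = 1.3 + 19.3 = 20.6 SD-months.

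A fading and a growing effect give the same area, so it cannot stand in for the change.

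**3. The plan's own power figures (protocol section 10.3).** Inputs: n = 120, taken as 60 per arm; two-sided 0.05; ANCOVA with one pre and two post measures. The variance factor is (1 + r_post)/2 − r_base², where r_post is the correlation between the two post measures and r_base is that of each with baseline.

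| Outcome | Correlations | Factor | Power at 0.35 / 0.40 / 0.50 SD | Stated |
|---|---|---|---|---|
| ADOS | 0.7 throughout | 0.85 − 0.49 = 0.36 | 89.2 / 95.5 / 99.5% | 89 / 96 / 99% |
| Language, adaptive | r_base 0.45, r_post 0.7 | 0.85 − 0.2025 = 0.6475 | 66.4 / 77.7 / 92.6% | 65 / 76 / 92% |
| Language, adaptive | 0.45 throughout | 0.725 − 0.2025 = 0.5225 | 75.6 / 85.8 / 96.6% | not reproduced |

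Two things follow. These powers are for an effect averaged over endpoint and follow-up, so they describe neither the follow-up difference nor the change. And the 0.45 in section 10.3 is a baseline-to-later correlation. For language and adaptive behaviour the endpoint-to-follow-up correlation is not stated; the power figures fit 0.7 better. No correlation is given for the DCMA.

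**4. Precision of the change.** With equal variances and equal baseline correlations at both occasions, baseline adjustment does not reduce the variance of the change. SE = √(2/60)·√(2(1−r)), where r is the endpoint-to-follow-up correlation and √(2/60) = 0.183.

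| r | SE | 95% CI half-width | Change detectable at 80% power | Power for a 0.25 SD fade |
|---|---|---|---|---|
| 0.7 | 0.141 | 0.28 | 0.40 | 42% |
| 0.45 (assumed) | 0.191 | 0.38 | 0.54 | 26% |

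**5. Illustration (invented effect sizes, r = 0.7 throughout).** The baseline-adjusted SE of the follow-up difference is 0.183·√(1 − 0.49) = 0.130, half-width 0.26.

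- Endpoint 0.40, follow-up 0.20: follow-up CI −0.06 to 0.46; change −0.20, CI −0.48 to 0.08. Neither loss nor maintenance is established.
- Endpoint 0.80, follow-up 0.40: follow-up CI 0.14 to 0.66; change −0.40, CI −0.68 to −0.12. An effect is clearly present, yet the point estimate has halved and the interval excludes no change.

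In both cases the follow-up figure alone leaves out what Objective 1 asks.

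**The case against.** The strongest reply is that nothing essential is missing. All three occasions are analysed jointly, and the model holds the term. Section 10.4 of the protocol states the aim and no later text withdraws it: Appendix 1, which lists major revisions, names only outcome changes. The SAP covers the primary follow-up paper, and it also omits the protocol's Stages 2 and 3, so silence does not prove that the aim was dropped. If sustained simply means that a difference still exists years later, the planned estimate answers Objective 1 directly. And a change contrast with 26-42% power for a 0.25 SD fade will often be inconclusive.

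Much of this stands, and it rules out three stronger readings. A reader might infer that the analysis is unable to tell a maintained effect from a faded one; it is able to, but the contrast is not named. A reader might infer that significance at follow-up is to be the test of sustained; no passage sets such a rule, and the SAP speaks of good estimates, an effect-size diagram and, in Appendix 2, confidence intervals. A reader might infer that the Stage 1 aim was abandoned; the text does not say so.

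What the reply does not do is point to a named estimate of the change. Stage 1 shows that the investigators wanted more than presence at follow-up, and the plan agreed before inspection by group does not specify it. Low precision is a reason to show the interval, not to leave the quantity unreported.

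**Conclusion.** The point holds as a gap between the protocol's aim and the SAP's named estimates, and it is cheap to close. It does not invalidate the planned analysis: the follow-up difference is a legitimate estimate and shows whether an effect is present. It does not show whether the effect was kept, reduced or enlarged, and the post-inspection area summary does not show it either.

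The likely precision of the missing estimate is a 95% CI half-width of about 0.28 SD, or 0.38 SD at the lower correlation. This assumes 60 per arm, equal variances, endpoint data only from those followed up, and an endpoint-to-follow-up correlation of 0.7 (documented for the ADOS only) or 0.45 (an assumption). The point is confined to Part A outcomes measured at endpoint and follow-up. Part B outcomes and the teacher VABS are analysed at follow-up only, so no change in effect can be formed for them.

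**What to change.** For each Part A outcome still reported with a treatment-effect model (ADOS CSS, child initiations, parent synchrony, parent VABS), report three quantities from the same fitted model, each with a 95% CI: the group difference at PACT endpoint, the group difference at the median follow-up age, and follow-up minus endpoint. Evaluate all three at the same covariate values. For the ADOS use the latent scale of the ordinal model, with the group effect on slope allowed to differ between the two pieces. The FLQ score is not included because Appendix 2 drops it.

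Add a sentence saying that Objective 1 is interpreted by estimation from the second and third quantities together. It should add that a non-significant follow-up difference will not be read as loss, nor a non-significant change as maintenance.

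Because the data have been inspected, list this in Appendix 2 as an addition that restores the Stage 1 aim, not as a contrast specified in advance.

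Cost: two further linear combinations for each DCMA and VABS outcome, somewhat more work for the ordinal ADOS model, and no new data. The drawback is that the change may be too imprecise to settle the question, and the report would have to say so.
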